#### 10. Data handling conventions

#### Premature Withdrawal and Missing Data

If any subject withdraws prematurely from the study (prior to the final visit D90±7 days assessment), they are required to complete the withdrawal visit in the CRF. The reasons for withdrawal will be presented in a summary table. For the purposes of summaries and analysis of clinic visit data, this visit will be assigned to the next scheduled clinic visit for that patient, regardless of whether the date falls within the next visit window.

Patients who withdraw before the end of the study, but who do provide at least one post-baseline measure for a particular endpoint, will be included in the analysis.

Patients who do not attend any visits after randomization will be excluded from analysis of efficacy outcomes and safety outcomes, as no post-baseline data will be available.

Missing data will not be imputed in the main analysis. Illogic data needs to be investigated by the data management facility, investigators or Sponsor together to identify possible reasons, and restrained by the parties in a data review meeting after full discussion: illogic data, if sufficient reasons have been found to indicate its incorrectness, should be removed, or otherwise, should be remained and subjected to analysis and the results obtained without such removed data should be treated as sensitivity analysis; If there is data collected in the study that is not in accordance with the program requirements such as planned external visits, it will be presented in a list, and descriptive or comparative analysis will be decided at the data review meeting depending on the specific situation of the data. In sensitivity analysis, multiple imputation was performed to impute the missing data of the primary efficacy outcome.

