### **Research Flow Chart**

Measures		Screening/B aseline	Treatment period			follow-up		
		4.5 h. (Before thrombolysi s)	0h (Thrombolytic Therapy)	24 h + 2 h	24h-36h	7±1 day or before discharge (whichever occurs first)	90±7 days/early end of visit	
	ing Informed Consent	X						
	emographic aracteristics	X						
Sympto	ms of this onset	X						
Med	dical history	X						
Prior	medication1	X						
	oncomitant ation/treatment 	X	X	X	X	X	X	
V	ital signs 	X	X	X		X		
	mRS	X 					X	
	NIHSS	X		X		X		
	BI scale						X	
EQ	- 5 D scale						X	
Blood/t	urine pregnancy	X						
	Routine blood test	X		X		X		
Labora	Blood biochemistry	X		X		X		
exami nation 	Coagulation function	X		X		X		
	Routine urinalysis			X		X		
	rocardiogram (ECG) 	X				X		
C	T or MRI 	X			X			
ran	domization	X						
	rombolysis formation 		X					
Advers	e Events/Serious dverse Events		X	X	X	X	X	

- 1. Prior medication is only recorded for drugs that fall into the restrictions in the inclusion/exclusion criteria.
- 2. The "blood pressure" of screening and enrollment is collected when vital signs are collected. "0h" is regarded as the monitoring results of vital signs within 5min before thrombolysis. Vital signs include blood pressure, pulse, body temperature and respiratory

rate

- 3. The mRS score at screening include pre-onset score and post-onset pre-thrombolysis score.
- 4. Blood/urine pregnancy test is applicable to fertile women only;
- 5. Laboratory examination:
  - 1) Baseline laboratory tests include routine blood test, blood biochemistry, and coagulation function; Subjects will not need to repeat the test if they have already performed some laboratory tests between the present onset and prior to thrombolysis. For baseline blood lipid tests (total cholesterol (TC), low density lipoprotein (LDL-C), high density lipoprotein (HDL-C), triglyceride (TG)), the most recent fasting blood lipid is collected after the onset of the disease. Blood glucose test is performed at baseline. Peripheral blood glucose is measured as one of the inclusion and exclusion criteria, and venous blood is collected for blood glucose test. Blood biochemical results are allowed to be obtained after the study drug has been administered. If abnormal blood biochemical results are obtained, they will be handled by the study physician in accordance with the discipline guidelines and the clinical management pathway of the hospital.

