## 8. Efficacy endpoints

## 8.1 Primary efficacy endpoints

The proportion of subjects with 90-day MRS score of 0-1: Proportion of subjects with 90-day MRS score of 0-1 to all enrolled subjects. Calculation formula:

The proportion of subjects with 90-day MRS score of 0-1 = the number of subjects with 90-day MRS score of 0-1 / the number of subjects enrolled in this group  $\times 100\%$ 

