#### 3. Study Endpoint(s)

Primary Efficacy Endpoints:

The proportion of patients with mRS score of 0-1 at 90 days.

Calculation formula:

The proportion of patients with 90-day mRS score of 0-1 = the number of patients with 90-day mRS score of 0-1 / the number of patients enrolled in this group  $\times 100\%$ .

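### The final SAP files a late withdrawal-visit mRS as the 90-day mRS, and its enrolled-patient denominator implies that a missing score is a non-response; both conflict with its rule of no imputation

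*Supplement*

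**What the plan says.** **Withdrawal visits.** SAP section 10 (Premature Withdrawal and Missing Data) requires a withdrawal visit from anyone leaving before day 90 and states, for summaries and analysis, that "this visit will be assigned to the next scheduled clinic visit for that patient, regardless of whether the date falls within the next visit". Those leaving early "but who do provide at least one post-baseline measure for a particular endpoint, will be included in the analysis".

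**Where mRS is collected.** Protocol 3.3 lists no visit between day 7±1 and day 90±7. In the protocol V2.2 Research Flow Chart the only post-baseline column with mRS marked is headed "90±7 days/early end of visit".

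**Missing data.** The same SAP section says: "Missing data will not be imputed in the main analysis". It excludes patients with no visit after randomization from efficacy analysis, and adds: "In sensitivity analysis, multiple imputation was performed to impute the missing data of the primary efficacy outcome".

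**Denominator.** The primary endpoint formula divides by "the number of patients enrolled in this group" in SAP section 3, and by "the number of subjects enrolled in this group" in protocol 8.1. Protocol 12.4 instead refers to enrolled patients within the data set being analysed.

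**Primary analysis.** SAP section 12 uses both the FAS and the per-protocol set (PPS), with a center-adjusted Cochran-Mantel-Haenszel test and an RR. It does not say which rule applies to a patient without an in-window day-90 score.

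**The concern.** Two separate groups of patients are affected.

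- **Withdrawn after the day-7/discharge visit, with an mRS at the withdrawal visit.** The next scheduled visit is day 90, so a day-10 score, for example, enters the FAS primary analysis as the 90-day score. That is a carry-forward in effect. Once filed, the score is no longer missing, so the multiple-imputation sensitivity analysis cannot test what it does to the result.
- **No mRS at all after baseline.** Under the section 3 formula such a patient stays in the denominator and cannot enter the numerator, which is non-response. Under section 10 nothing is imputed, so the patient drops out of the RR.

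These rules decide who is counted, and with which score, in the single confirmatory test. The margin is an RR of 0.937, only 6.3% below 1. Two statisticians following the SAP faithfully could report different primary RRs. In an open-label trial, departures that differ by arm are conceivable.

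**Working it through.** **Inputs from SAP sections 4 and 6:** margin 0.937; one-sided α 0.025; power 85%; control rate 59.32%; RR 1.07; 10% dropout; 642 evaluable and 715 randomized per arm. The splits of missingness, the share of early scores and their success rates are not in the documents; they are assumptions.

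**Formula (log-RR Wald).** With n per arm and rates pT and pC:

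SE = √{[(1−pT)/pT + (1−pC)/pC]/n}; power = Φ{[ln(pT/pC) − ln 0.937]/SE − 1.96}.

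**1. The plan's own figure.** pC = 0.5932 and pT = 1.07 × 0.5932 = 0.6347. The required n is 642.8 by this formula and 641.98 by Farrington-Manning, so 642 is reproduced. Inflation gives 642/0.9 = 714 after rounding up, against 715 stated, an immaterial difference. The method takes the 10% out of the analysis; it is a complete-case calculation.

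**2. Complete cases, n = 642.** SE = √(1.2613/642) = 0.0443. ln 1.07 − ln 0.937 = 0.1327. 0.1327/0.0443 − 1.96 ≈ 1.03, so power is 85.0%.

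**3. Formula denominator, 10% missing in each arm, n = 715.** The rates become 0.9 × 0.6347 = 57.1% and 0.9 × 0.5932 = 53.4%. The RR is still 1.07. SE = √(1.6236/715) = 0.0477. 0.1327/0.0477 − 1.96 ≈ 0.83, so power is about 79.5%.

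**4. Formula denominator, unequal missingness (assumed).** The RR is multiplied by (1−mT)/(1−mC). The true RR is set at the margin of 0.937, n = 715:

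| Missing, test vs control | Factor | Apparent RR | One-sided type I error |
|---|---|---|---|
| 10% vs 10% | 1.000 | 0.937 | 2.5% |
| 9% vs 11% | 0.91/0.89 = 1.022 | 0.958 | 6.4% |
| 8% vs 12% | 0.92/0.88 = 1.045 | 0.980 | 13.8% |

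The opposite imbalance works against the test drug: at 12% vs 8%, a true RR of 1.07 appears as 1.07 × 0.88/0.92 = 1.023.

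**5. Early score filed as day 90, balanced (assumed).** A share w in each arm has the same early mRS 0-1 rate q. The apparent RR is [(1−w) × 0.937 × 0.5932 + wq] / [(1−w) × 0.5932 + wq], with n = 715:

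| w | q | Apparent RR | Type I error |
|---|---|---|---|
| 2% | 20% | 0.937 | 2.6% |
| 5% | 40% | 0.939 | 2.8% |
| 10% | 40% | 0.941 | 3.1% |

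**6. Early score filed as day 90, unbalanced (assumed).** With 7% substituted in the test arm against 3% in the control arm, and early success 25 points lower, a true RR of 1.00 becomes (0.5932 − 0.07 × 0.25)/(0.5932 − 0.03 × 0.25) = 0.983. That is 0.017/0.063 = 27% of the distance to the margin, in the direction against the test drug.

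Items 3 to 6 are alternative scenarios. The same 10% cannot be both wholly missing and wholly substituted, so the effects must not be added.

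**The case against.** The strongest reply is that the PPS contains the damage. SAP section 7 keeps patients with a missing primary endpoint out of the PPS and lists serious overrun of the follow-up window as a violation; protocol 12.1 also names visits out of window. A day-10 score would therefore generally leave the PPS, subject to data review. This stands, and it confines both problems largely to the FAS. It does not remove them, because the FAS carries the primary analysis alongside the PPS.

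Second, the enrolled-patient wording may be generic. The Event Rates formula in SAP section 10 uses it too, protocol 12.4 ties the denominator to the data set, and no text calls a missing score a failure. That is fair: non-response follows from the arithmetic of the formula and is not a declared rule. The conflict still needs one sentence to settle it.

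Third, the reach of the reassignment rule is narrow. A withdrawal before the day-7/discharge visit maps to a visit with no scheduled mRS, and a patient lost without a withdrawal visit has nothing to reassign. This stands, although the flow chart puts every early-end visit in the day-90 column.

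Several stronger readings are tempting but unsupported:
- A reader might infer that one patient can be analysed three ways under stated rules. A patient whose early score is filed as day 90 is not also missing; the denominator question concerns other patients.
- A reader might infer that missing-as-failure discards the 642 evaluable patients. They remain, and the analysed number rises to 715.
- A reader might infer a built-in bias toward non-inferiority. Balanced missing-as-failure leaves the RR unchanged and costs only power, and balanced substitution adds at most 0.6 points of type I error in the range examined. Larger distortion needs an imbalance between arms, which the documents neither state nor imply.

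**Conclusion.** The point holds as a should-fix. The final SAP contains a visit-assignment rule that works as a carry-forward in the FAS and shields the affected scores from the multiple imputation. It also contains a denominator that conflicts with its own missing-data rule and with the basis of its sample size.

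The firmest figure uses only the plan's inputs: power of 85.0% on evaluable patients against about 79.5% under the written formula at 10% dropout. The type I error of about 6.4% rests on an assumed 9% vs 11% split. The 2.6-3.1% for early scores rests on an assumed 2-10% substituted, with common early success rates of 20-40%. Of the two problems, the unresolved denominator is the larger. The stated sample size is not in error.

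**What to change.** 1. **SAP section 10:** keep the reassignment rule for listings only. Admit a withdrawal-visit mRS to the day-90 endpoints only if it falls within 90±7 days, and count known deaths as mRS 6.
2. **Multiple imputation:** treat the remaining day-90 scores as missing, and use early mRS and NIHSS as predictors.
3. **SAP section 3 and protocol 8.1:** state the primary denominator as FAS patients with a 90-day mRS or a known death, and align protocol 12.4 with it.
4. **Sensitivity analysis:** add missing-as-failure.

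The cost is a few sentences in the SAP and a one-line protocol clarification. A few more values become missing and pass to the imputation already planned. No new data collection or change of sample size is needed. The wording should be settled before unblinding.

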#### 3.3 Visits

Study visit points: -4.5h-0h (before thrombolysis), 0h (thrombolytic therapy), 24h±2h, 24h-36h, 7±1 day, 90±7 days (end visit).

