and thrombolysis, antiplatelet and anticoagulant therapy should be continued according to the bleeding degree.

In particular, symptomatic intracranial hemorrhage (2%-7%). The vast majority of symptomatic intracranial hemorrhage occur within 24 hours of thrombolytic therapy. The symptoms include sudden changes in the state of consciousness, single or multiple location signs of the nervous system, coma, headache, nausea, vomiting and seizures, hypertensive emergency, and rapid death in some cases. When this happens, active measures should be taken:

- (1) Stop thrombolysis, antiplatelet and anticoagulant therapy immediately.
- (2) Perform imaging examination (emergency CT or MRI) to determine the location, amount and classification of intracranial bleeding.
  - (3) Measure erythrocyte volume, hemoglobin, prothrombin, activated partial thromboplastin time, platelet count, fibrinogen, D-dimer, blood group and perform a cross-match test.
  - (4) Reduce intracranial pressure, including proper control of blood pressure, raising the head of the bed by 30 degrees, intravenous mannitol, endotracheal intubation and auxiliary ventilation, surgical hematoma removal, decompression of bone flap and ventricle puncture and drainage when necessary.
  - (5) If necessary, use reverse thrombolysis, antiplatelet and anticoagulant drugs: 2U of fresh frozen plasma should be given every 6 hours within 24h; it is recommended to neutralize with protamine (1mg protamine to neutralize 100U of normal heparin) for patients who have used normal heparin therapy within 4h. If the bleeding time is abnormal, 6-8U of platelets can be transfused.
  - (6) Properly control the blood pressure.

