#### Full Analysis Set (FAS):

According to the basic principle of intention-to-treat (ITT), all patients who were enrolled, randomized and had the record of at least one-day treatment of study drugs will be included. This population was also referred as modified ITT population.

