#### Safety Set (SS)

All patients who received at least 1-time of study drug according to the study protocol and safety assessment available will be included in the safety population. Throughout the safety results sections, erroneously treated patients (eg, those randomized to rhTNK-tPA group but actually given rhTNK-tPA) will be accounted for in the actual treatment group. This population will be used for safety analyses.

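### The SAP excludes patients with no visit after randomization and makes no exception for death; if “visit” means a follow-up visit, deaths before 24 hours drop out of efficacy and safety

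*Supplement*

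**What the plan says.** The final SAP, section 10 (Premature Withdrawal and Missing Data), reads: "Patients who do not attend any visits after randomization will be excluded from analysis of efficacy outcomes and safety outcomes", with the reason "as no post-baseline data will be available". The same section says that missing data are not imputed in the main analysis, and limits multiple imputation to a sensitivity analysis of the primary efficacy outcome.

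Other places bear on who this sentence reaches:

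- **FAS (SAP section 7):** "all patients who were enrolled, randomized and had the record of at least one-day treatment of study drugs will be included". There is no visit condition.
- **Safety Set (SAP section 7):** "All patients who received at least 1-time of study drug according to the study protocol and safety assessment available will be included". The next sentence counts erroneously treated patients under the treatment actually given.
- **Denominators (SAP section 3 and section 10, Event Rates):** the primary proportion and the event rates are both divided by the number enrolled in the group.
- **Visits (protocol 3.3):** "Study visit points: -4.5h-0h (before thrombolysis), 0h (thrombolytic therapy), 24h±2h, 24h-36h, 7±1 day, 90±7 days (end visit"). Protocol 7.4 (Follow-up) begins at the 24 h assessment.
- **Adverse events (protocol 9.1.2):** recording starts at dosing.
- **mRS (protocol Annex 3):** grade 6 is death. No SAP sentence says that a death before day 90 is scored 6 and kept.

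**The concern.** In a thrombolysis trial the first day carries much of the treatment-related harm. Protocol 9.7 says so: "The vast majority of symptomatic intracranial hemorrhage occur within 24 hours of thrombolytic therapy", and adds that some of these patients die rapidly. A patient who is dosed and dies at 10 h attends no follow-up visit. Read with follow-up visits in mind, the SAP sentence removes that patient from every efficacy and safety analysis. The stated reason is untrue for such a patient, who has a fatal adverse event on record, a known day-90 mRS and a mortality event.

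Two consequences follow on that reading. Removing non-responders raises the response proportion of the arm they leave, so an arm with more early deaths looks better on the primary endpoint. Mortality and sICH lose cases in any arm where they occurred early, even when the arms are balanced. Nothing later in the SAP restores them, because the imputation analysis does not touch the safety endpoints.

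**Working it through.** **1. The plan's own figure.** Inputs from SAP section 6: control 59.32%, RR 1.07, margin 0.937, one-sided α 0.025, power 0.85. On the log-RR scale

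n = [(1−pT)/pT + (1−pC)/pC] × (1.960 + 1.036)² / (ln 1.07 − ln 0.937)²

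with pT = 1.07 × 0.5932 = 0.6347. This gives 642.8, or 643 per arm. The Farrington-Manning score version gives 642, the SAP's figure. Dividing 642 by 0.9 gives 714, against 715 stated. The sample size reproduces and is not affected by this point.

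**2. What each reading of a visit does.**

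| Reading | Who is excluded | Consequence |
|---|---|---|
| Follow-up visit, first at 24±2 h | Adds treated patients who die before 24 h | Contradicts the FAS and the enrolled-patient denominators; the stated reason is false for them |
| Any visit point, including 0 h dosing | Only patients randomized but not dosed | Redundant: FAS and Safety Set already require dosing |

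**3. Effect on the primary RR.** Early deaths are non-responders, so dropping dT and dC of them changes only the denominators. The RR is multiplied by (715 − dC)/(715 − dT). The counts are assumptions.

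| Early deaths, tenecteplase vs alteplase | Factor |
|---|---|
| equal | 1.000 |
| 7 vs 4 | 711/708 = 1.004 |
| 7 vs 0 | 715/708 = 1.010 |
| 14 vs 7 | 708/701 = 1.010 |

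If the imbalance runs the other way, the factor is the reciprocal and favours alteplase. At the planned RR of 1.07, a factor of 1.0099 is a shift of 0.0106, about 8% of the distance to the margin (1.07 − 0.937 = 0.133). Measured from RR 1.00 it is 0.0099/0.063, about 16%.

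**4. Can it change the decision?** Only near the boundary. Take 432 vs 424 responders of 715 per arm, RR 432/424 = 1.019, with a Wald interval on log RR:

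| Early deaths dropped | Lower 95% limit | Against 0.937 |
|---|---|---|
| none | 0.9359 | fails |
| 4 vs 4 | 0.9363 | fails |
| 7 vs 4 | 0.9404 | passes |
| 14 vs 14 | 0.9371 | just passes |
| 14 vs 7 | 0.9462 | passes |

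**5. Effect on sICH in one arm.** Protocol 9.7 quotes 2% to 7%, that is about 14 to 50 of 715. The number of early fatal cases lost is assumed.

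| sICH with all kept | Early fatal cases lost | sICH after exclusion |
|---|---|---|
| 14/715 = 1.96% | 3 | 11/712 = 1.54% |
| 14/715 = 1.96% | 7 | 7/708 = 0.99% |
| 50/715 = 6.99% | 10 | 40/705 = 5.67% |
| 50/715 = 6.99% | 25 | 25/690 = 3.62% |

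The larger losses are extremes: they require half of all sICH to be fatal before the 24 h visit.

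**The case against.** The strongest reply is that the SAP says visits, not follow-up visits. Protocol 3.3 lists 0 h thrombolysis as a visit point, and the flow chart gives it its own column after randomization, with adverse-event recording. Every treated patient has then attended a visit. The stated reason also does not describe a patient with a recorded fatal event. Other provisions assume that deaths are counted: 90-day mortality is an endpoint, the Clinical Event Committee verifies deaths and sICH (protocol 3.7), and the SAP calls for a narrative of every death.

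This stands in part. A reader might infer that the SAP expressly deletes early deaths and fatal hemorrhages. It does not say so; that result depends on how the undefined word is read. But the benign reading leaves the sentence with nothing to do. The protocol also separates treatment (7.3) from follow-up (7.4), and takes the 0 h vital signs before thrombolysis, so a rule justified by absent post-baseline data fits follow-up visits more naturally.

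Two other inferences should not be drawn. First, that half of sICH would vanish: the protocol says that most sICH occurs within 24 h, not that most of it is fatal by then, and survivors reach the 24 h visit. Second, that the Safety Set removes misdosed patients: its wording about drug given according to protocol invites this, but the next sentence keeps erroneously treated patients, and protocol 12.1 has no such condition. That is an alignment matter only.

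**Conclusion.** The concern holds as a defect of an operative rule. The sentence contradicts the FAS definition and the enrolled-patient denominators, has no exception for death, and on its more natural reading removes treated patients who die before 24 h from the primary endpoint, mortality and sICH. On the other reading it is redundant.

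The size cannot be derived from the documents, which give no count of deaths before 24 h. Assuming 0 to 7 excess early deaths in one arm of 715, the bias in the RR is 0% to 1.0% toward the arm with more early deaths. That is small against the planned distance to the margin and decisive only near the boundary. The undercount of early deaths and early fatal sICH is potentially larger in relative terms and does not need an imbalance between arms.

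**What to change.** In SAP section 10, delete the sentence, or limit it to patients with no outcome information and unknown vital status. Then state that:

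- every treated patient stays in the FAS and the Safety Set;
- any death to day 90 is scored mRS 6 and counted in 90-day mortality;
- such a death is also counted as sICH if so adjudicated.

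As a secondary alignment, remove the condition of drug given according to the study protocol from the Safety Set definition, so that it agrees with its own next sentence and with protocol 12.1. Note there that a recorded death or serious adverse event counts as a safety assessment.

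The cost is SAP wording. The data are already collected, and the sample size does not change.
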